#### **GASTROINTESTINAL TOXICITY**

Diarrhea and colitis have been associated with the administration of Cobimetinib plus Atezolizumab. Diarrhea can frequently be managed with anti-diarrheal agents but can also progress to clinically significant dehydration and/or electrolyte imbalances with effects on other organs, possibly resulting in renal, hepatic, and/or cardiac failure. Patients should be instructed to promptly contact the investigators if they develop diarrhea. Investigators should treat diarrhea and intervene promptly for patients who appear to be at increased risk of developing significant dehydration, electrolyte imbalances, and/or multi-organ failure. Patients should receive maximum supportive care per institutional guidelines.

## **HEPATOTOXICITY**

Hepatotoxicity has been associated with the administration of atezolizumab and cobimetinib. Eligible patients must have adequate liver function, as manifested by measurements of total bilirubin and hepatic transaminase, and liver function will be monitored throughout study treatment.

While in this study, patients presenting with right upper-quadrant abdominal pain and/or unexplained nausea or vomiting should have liver function tests (LFTs) performed immediately and reviewed before administration of the next dose of study drug.

If LFTs increase, neoplastic, concurrent medications, viral hepatitis, and toxic etiologies should be considered and addressed, as appropriate. Imaging of the liver, gall bladder, and biliary tree should be performed to rule out neoplastic or other causes for the increased LFTs. Anti-nuclear antibody, perinuclear anti-neutrophil cytoplasmic antibody, anti-liver kidney microsomal antibodies, and anti-smooth muscle antibody tests should be considered.

## **DERMATOLOGIC TOXICITY**

Treatment-emergent rash has been associated with atezolizumab and cobimetinib. The majority of the cases of rash were mild in severity and self-limited, with or without pruritus. Although uncommon, cases of severe cutaneous adverse reactions such as Stevens-Johnson syndrome and toxic epidermal necrolysis have been reported with atezolizumab.

## **PULMONARY TOXICITY**

Mild-to-moderate events of pneumonitis have been reported with atezolizumab and cobimetinib. All pulmonary events should be thoroughly evaluated for other commonly reported etiologies such as pneumonia/infection, lymphangitic carcinomatosis, pulmonary embolism, heart failure, chronic obstructive pulmonary disease, or pulmonary hypertension:

- Measurement of oxygen saturation (i.e., arterial blood gas)
- High-resolution computed tomography (CT) scan of the chest
- Bronchoscopy with bronchoalveolar lavage and biopsy (if clinically feasible)
- Pulmonary function tests (diffusion capacity of the lung for carbon monoxide)
- Pulmonary function testing with a pulmonary embolism protocol

Patients will be assessed for pulmonary signs and symptoms throughout the study. Patients will also have CT scans of the chest at every tumor assessment. Chest CT should be reviewed for pulmonary toxicities as well as for disease status.

## **OCULAR TOXICITY**

An ophthalmologist should evaluate visual complaints.

Uveitis or episcleritis and other immune-mediated ocular disease may be associated with atezolizumab and may be treated with topical corticosteroid eye drops. Atezolizumab should be permanently discontinued for immune-mediated ocular disease that is unresponsive to local immunosuppressive therapy.

Serous retinopathy have been associated with cobimetinib.

## **DECREASED LEFT VENTRICULAR EJECTION FRACTION (LVEF)**

Decreased LVEF has been seen with cobimetinib. Permanent discontinuation of cobimetinib treatment should be considered if cardiac symptoms are attributed to cobimetinib and do not improve after temporary interruption.

Decreased LVEF may also result from immune related cardiomyopathy, a potential risk of atezolizumab therapy. For this reason, atezolizumab & CDX-1127 (varlilumab) should also be held in the setting of decreased LVEF, pending the results of a cardiac workup. This work up should generally include troponin, CPK, cardiac MRI, EKG, and cardiology consultation. Atezolizumab & CDX-1127 (varlilumab) may be restarted on a case-by-case basis as long as LVEF is > 40% (or  $\leq$  10% absolute decrease from BL) and myocarditis has been excluded. For patients with more severe reductions in the LVEF, atezolizumab & CDX-1127 (varlilumab) may be restarted only if the patient is clinically stable, and after consultation with the trial PI.

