|  |   | 
decreased LVEF can be confidently attributed to a non-immune-mediated etiology, LVEF is > 40% (or <math>\leq</math> 10% absolute decrease from BL) and myocarditis has been excluded, resumption of atezolizumab & CDX-1127 (varlilumab) at fixed dose can be considered on case by case basis with discussion & approval by trial PI. For patients with more severe reductions in the LVEF, atezolizumab & CDX-1127 (varlilumab) may be restarted only if the patient is clinically stable, and after consultation with the trial PI.
 | 
baseline LVEF is more than 10%
 
*If etiology of decreased LVEF can be confidently attributed to cobimetinib alone or a non-immune-mediated etiology, LVEF is > 40% (or <math>\leq</math> 10% absolute decrease from BL) and myocarditis has been excluded, resumption of atezolizumab & CDX-1127 (varlilumab) at fixed dose can be considered on case by case basis with discussion & approval by trial PI. For patients with more severe reductions in the LVEF, atezolizumab & CDX-1127 (varlilumab) may be restarted only if the patient is clinically stable, and after consultation with the trial PI.
 |
|  | Symptomatic LVEF decrease from baseline | 
Withhold atezolizumab & CDX-1127 (varlilumab) for up to 4 weeks; repeat LVEF
 
Work up should generally include troponin, CPK, EKG, echocardiogram and/or cardiac MRI, and cardiology consultation
 
Resume atezolizumab & CDX-1127 (varlilumab) at fixed dose if all of the following are present
 
 
• Symptoms
 
   | 
Withhold atezolizumab & CDX-1127 (varlilumab) and cobimetinib for up to 4 weeks; repeat LVEF
 
Work up should generally include troponin, CPK, EKG, echocardiogram and/or cardiac MRI, and cardiology consultation
 
Resume atezolizumab & CDX-1127 (varlilumab) at fixed dose and cobimetinib at next
   |

|  |  |  |   |
|--|--|--|---|

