|  |  | 
resolved, and
 
 
• LVEF is 50% or greater, OR
 
• Absolute decrease from baseline LVEF is 10% or less
 
 
Permanently discontinue atezolizumab & CDX-1127 (varlilumab)* if any of the following are present
 
 
• Symptoms persist, or
 
• Symptoms resolved, but LVEF is less than 50% and Absolute decrease from baseline LVEF is more than 10%
 
 
* If etiology of decreased LVEF can be confidently attributed to a non-immune-mediated etiology, LVEF is > 40% (or <math>\leq</math> 10% absolute decrease from BL) and myocarditis has been excluded, resumption of atezolizumab & CDX-1127 (varlilumab) at fixed dose can be considered on case by case basis with discussion & approval by trial PI. For patients with more severe reductions in the LVEF, atezolizumab & CDX-1127 (varlilumab) may be restarted only if the patient is clinically stable, and after
 | 
lower dose if all of the following are present
 
 
• Symptoms resolved, and
 
• LVEF is 50% or greater, OR
 
• Absolute decrease from baseline LVEF is 10% or less
 
 
Permanently discontinue atezolizumab & CDX-1127 (varlilumab)* and cobimetinib any of the following are present
 
 
• Symptoms persist, or
 
• Symptoms resolved, but LVEF is less than 50% and Absolute decrease from baseline LVEF is more than 10%
 
 
*If etiology of decreased LVEF can be confidently attributed to cobimetinib alone or a non-immune-mediated etiology , LVEF is > 40% (or <math>\leq</math> 10% absolute decrease from BL) and myocarditis has been excluded, resumption of atezolizumab & CDX-1127 (varlilumab) at fixed dose can be considered on case by case basis with discussion & approval by trial PI. For patients with more severe reductions in the LVEF,
 |
|--|--|--|---|

|                                 |   |   |   |
|---------------------------------|---|---|---|
|                                 |   | consultation with and approval from the trial PI.   | atezolizumab & CDX-1127 (varlilumab) may be restarted only if the patient is clinically stable, and after consultation with and approval from the trial PI.   |

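### For Arm A patients with a symptomatic LVEF decrease, Section 7.2.2 lacks the trial PI approval and the firm cobimetinib stop that Section 7.3 requires

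*Combined protocol and SAP*

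**What the plan says.** Two places tell an Arm A site what to do after a symptomatic fall in LVEF.

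**Section 7.2.2, Decreased LVEF paragraph.** Atezolizumab and varlilumab are held during a cardiac work-up. They "may be restarted on a case-by-case basis as long as LVEF is > 40" percent (or the absolute drop from baseline is at most 10%) and myocarditis has been excluded. For larger reductions the patient must be clinically stable and the trial PI consulted. On cobimetinib: "Permanent discontinuation of cobimetinib treatment should be considered if cardiac symptoms are attributed to cobimetinib and do not improve after temporary interruption".

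**Section 7.3, symptomatic LVEF row, Arm A column.** All three agents are withheld for up to 4 weeks, LVEF is repeated and a cardiac work-up is listed.
- Resume list: all three may resume, cobimetinib one level lower, if symptoms have resolved and either LVEF is at least 50% or "Absolute decrease from baseline LVEF is 10% or less".
- Stop list: all three are permanently discontinued if symptoms persist, or in the case "Symptoms resolved, but LVEF is less than 50% and Absolute decrease from baseline LVEF is more than 10" percent.
- Starred note: the antibodies alone may come back if the decrease "can be confidently attributed to cobimetinib alone or a non-immune-mediated etiology", LVEF is above 40% (or the drop is at most 10%) and myocarditis is excluded. Resumption then "can be considered on case by case basis with discussion" and approval by the trial PI.
- Larger reductions: the antibodies "may be restarted only if the patient is clinically stable, and after consultation with and approval from the trial PI".

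The starred note of the asymptomatic row, like 7.2.2, asks only for consultation in that last case: "may be restarted only if the patient is clinically stable, and after consultation with the trial PI".

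**The concern.** The same patient can be managed in two ways, depending on which section the site opens. Under 7.2.2 a site could give the antibodies again after a symptomatic cardiac event without the trial PI having agreed, and could keep cobimetinib open as an option. Under 7.3 it could do neither. The triplet is first in human (Section 2.3.4), and 7.2.2 itself names immune-related cardiomyopathy as a potential risk of atezolizumab. What is at stake is the safety of an individual patient; the primary endpoints and their analysis are not affected.

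**Working it through.** No figure in the plan needs to be reproduced. The check sets the two texts side by side, finds where they diverge, and gauges how often that could happen.

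**1. The rules compared, where the 7.3 stop list applies**

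| Element | 7.2.2 paragraph | 7.3 symptomatic row |
|---|---|---|
| Antibodies, default | restart case by case | permanent stop |
| LVEF needed for return | above 40%, or drop of 10 or less | same |
| Myocarditis excluded | required | required (starred note) |
| Attribution | not in the paragraph; the 7.2.2 lead-in requires it | confident, to cobimetinib alone or a non-immune cause |
| Trial PI | no step | discussion and approval |
| Cobimetinib, symptoms persist | permanent stop to be considered | permanent stop |
| Cobimetinib, symptoms resolved | silent | permanent stop |

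**2. The LVEF range affected when symptoms have resolved.** I read the 10% absolute decrease as percentage points. Eligibility requires LVEF above 50% (Section 3.1.5), so a drop of 10 points or less always leaves LVEF above 40%, and the 7.2.2 threshold reduces to LVEF above 40%. The 7.3 stop applies when LVEF is below min(50, baseline − 10). Both hold when 40 < LVEF < min(50, baseline − 10). In whole numbers:

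| Baseline | min(50, baseline − 10) | LVEF values affected |
|---|---|---|
| 51% | 41 | none |
| 52% | 42 | 41% |
| 55% | 45 | 41–44% |
| 60% or more | 50 | 41–49% |

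If symptoms persist, the texts differ at any LVEF above 40%.

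**3. Two worked patients.** In both, baseline LVEF is 60%, myocarditis is excluded and the cause is clearly cobimetinib.
- *Symptoms resolved, LVEF 45%.* The drop is 60 − 45 = 15 points. 7.2.2 allows the antibodies to restart with no PI step and says nothing on cobimetinib. 7.3 stops all three (45 < 50 and 15 > 10), and the antibodies return only with PI approval.
- *Symptoms persist after interruption, LVEF 52%.* 7.2.2 allows the antibodies to restart and asks that a cobimetinib stop be considered. 7.3 stops all three, with the antibodies recoverable only through the starred note.

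**4. Does the protocol say which text governs?** Section 7.2.1 places the algorithms in 7.3 to standardize management, but describes them as suggested. The 7.2.2 lead-in requires each event to be assessed as due to targeted therapy or immunotherapy, and sends resumption to 7.3 when the cause is ambiguous. That settles the ambiguous case. It does not settle the case where the cause is clear. The elevated-CPK paragraph that follows in 7.2.2 refers expressly to 7.3; the LVEF paragraph does not.

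**5. Expected number of cases.** The protocol gives no rate for this triplet. Assume that rates from other regimens carry over to the 32 Arm A patients (Section 9.2):
- 0.8% symptomatic LVEF decrease with cobimetinib plus vemurafenib (Section 2.2.2.2.3): 0.008 × 32 = 0.26.
- Heart failure listed below 3% for cobimetinib (Section 10.1.1.3): 0.03 × 32 = 0.96 as a ceiling.

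These count all symptomatic cases. Those handled differently by the two texts are a subset.

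**The case against.** The strongest reply is that the texts never force a breach. 7.2.2 is permissive throughout, so a site that follows the 7.3 stop list also complies with 7.2.2. Section 7.2.1 further suggests that 7.3 was meant as the working dosing text. This stands, and it limits the point: a site goes wrong only by relying on the 7.2.2 paragraph alone. The converse also holds, since a site following 7.2.2 can omit steps that 7.3 makes mandatory.

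Three stronger readings are tempting and are not supported.

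- *A reader might infer that 7.2.2 allows restart with no thought of attribution.* The lead-in requires attribution and routes ambiguous causes to 7.3. If the cause is clearly cobimetinib or non-immune, the 7.3 attribution condition is already met, which leaves PI approval and the cobimetinib stop. A clearly immune cause falls to the immune-event rules of 7.1.1 and 7.1.2, and the point does not rest on it.
- *A reader might infer that 7.3 lets all three agents resume while myocarditis is still an open question*, for example at baseline 60%, LVEF 52% and symptoms resolved. The resume list does not repeat the exclusion. But 7.1.2 calls for urgent evaluation of possible myocarditis and treatment under its table when no other cause is found. The 7.3 row lists the work-up before the resume list, and the 7.3 myocarditis row stops all three agents at Grades 2–4. What remains is a drafting gap.
- *A reader might infer that 7.2.2 requires myocarditis to be excluded before any antibody restart.* Its sentence on more severe reductions does not state that condition.

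It can also be said that the PI will hear of such events anyway: symptomatic heart failure with reduced LVEF is an unacceptable toxicity in the run-in (9.5.1) and a cobimetinib event of special interest (10.3.4), and expedited reports reach the PI (10.3.2). That is notification, not approval before restart.

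**Conclusion.** The point holds, as a minor safety alignment. When the cause is clear, two differences are firm: 7.3 requires trial PI approval before the antibodies return and 7.2.2 does not at LVEF above 40%; and 7.3 requires cobimetinib to stop permanently where 7.2.2 asks only that this be considered, or is silent once symptoms resolve. The myocarditis exclusion missing from the 7.3 resume list, and consultation versus consultation plus approval for larger reductions, are lesser matters of wording.

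The LVEF ranges rest on reading the 10% as percentage points and on a baseline above 50%. The estimate of fewer than one symptomatic case rests on rates borrowed from other regimens. The case for changing the text rests on the consequence for a single patient, not on frequency.

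**What to change.** At the next amendment:

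1. State in the 7.2.2 LVEF paragraph that the LVEF rows of 7.3 govern stopping and restarting all agents in Arm A. Do this together with correcting the asymptomatic row, which now resumes treatment on a drop above 10% and stops it at LVEF of 50% or more with such a drop. 7.3 cannot govern until those lists are right.
2. Add to the resume lists of both LVEF rows that the work-up is complete and myocarditis excluded.
3. For more severe reductions, require both consultation with and approval by the trial PI in 7.2.2 and in both starred notes. State there that myocarditis must be excluded. In 7.2.2 this is a new condition for that case.

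The cost is a text edit; no test is needed beyond the work-up already listed. Sites lose a little discretion, and a restart may have to wait for that work-up to finish.

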## **ELEVATED CPK**

Elevated CPK has been reported with cobimetinib. Recommended Dose Modifications for Cobimetinib in Patients with CPK Elevations are presented below in section 7.3.

## **HEMORRHAGE**

Bleeding complications have been associated with cobimetinib treatment. There is no data on the effectiveness of cobimetinib dose modification for hemorrhagic events.

### **7.3 AE Management and Dose Interruption/Modification Guidelines**

| AE Management and Dose Interruption Guidelines for Specific Toxicities |                         |   |   |
|--|-------------------------|---|---|
| Toxicity   | Severity/
Duration   | Management  |   |
|  |                         | CDX-1127 (varlilumab)
& Atezolizumab   | Cobimetinib plus
CDX-1127 (varlilumab)
& Atezolizumab   |
| Abdominal pain   | Acute
abdominal pain | Symptoms of abdominal pain associated with elevations of amylase and lipase, suggestive of pancreatitis, have been associated with administration of other immunomodulatory agents. The differential diagnosis of acute abdominal pain should include pancreatitis. Appropriate workup should include an evaluation for | Symptoms of abdominal pain associated with elevations of amylase and lipase, suggestive of pancreatitis, have been associated with administration of other immunomodulatory agents. The differential diagnosis of acute abdominal pain should include pancreatitis. Appropriate workup should include an evaluation for |

|   |                        |   |  |
|---|------------------------|---|--|
|   |                        | 
obstruction, as well as serum amylase and lipase tests. See the guidelines for “Amylase and/or lipase increase” and “Immune-related pancreatitis” elsewhere in this table, as needed.
 
Right upper-quadrant abdominal pain and/or unexplained nausea or vomiting should be evaluated for potential hepatotoxicity (see the “Hepatotoxicity” guideline elsewhere in this table).
  | 
obstruction, as well as serum amylase and lipase tests. See the guidelines for “Amylase and/or lipase increase” and “Immune-related pancreatitis” elsewhere in this table, as needed.
 
Right upper-quadrant abdominal pain and/or unexplained nausea or vomiting should be evaluated for potential hepatotoxicity (see the “Hepatotoxicity” guideline elsewhere in this table).
   |
| Adrenal insufficiency *
Hypophysitis (pan-hypopituitarism) | Grade 2+ (symptomatic) | 
Hold Atezolizumab & CDX-1127 (varlilumab)
 
Refer patient to endocrinologist.
 
Perform appropriate imaging.
 
Initiate treatment with 1–2 mg/kg/day intravenous methylprednisolone or equivalent and convert to 1–2 mg/kg/day oral prednisone or equivalent upon improvement.
 
If event resolves to grade 1 or better and patient is stable on replacement therapy (if required) within 12 weeks, taper corticosteroids and resume atezolizumab & CDX-1127 (varlilumab) according to the guidelines above.
 | 
Hold Atezolizumab & CDX-1127 (varlilumab) and cobimetinib
 
Refer patient to endocrinologist.
 
Perform appropriate imaging.
 
Initiate treatment with 1–2 mg/kg/day intravenous methylprednisolone or equivalent and convert to 1–2 mg/kg/day oral prednisone or equivalent upon improvement.
 
If event resolves to grade 1 or better and patient is stable on replacement therapy (if required) within 12 weeks, taper corticosteroids and resume Atezolizumab & CDX-1127 (varlilumab)
 |

|                                 |              |   |   |
|---------------------------------|--------------|---|---|
|                                 |              | 
For recurrent hypophysitis, treat as a Grade 4 event.
 
Permanently discontinue atezolizumab & CDX-1127 (varlilumab) if event does not resolve to grade 1 or better or patient is not stable on replacement therapy within 12 weeks.
  | 
and cobimetinib at same doses
 
For recurrent hypophysitis, treat as a Grade 4 event.
 
Permanently discontinue atezolizumab & CDX-1127 (varlilumab) and cobimetinib if event does not resolve to grade 1 or better or patient is not stable on replacement therapy within 12 weeks.
                                       |
| Amylase and/or lipase increased | Grade 1      | 
Continue atezolizumab & CDX-1127 (varlilumab).
 
Monitor amylase and lipase prior to dosing.
  | 
Continue atezolizumab & CDX-1127 (varlilumab) and cobimetinib.
 
Monitor amylase and lipase prior to dosing.
  |
|                                 | Grade 2      | 
Continue atezolizumab & CDX-1127 (varlilumab).
 
Monitor amylase and lipase weekly.
 
For prolonged elevation (e.g., >3 weeks), consider treatment with 10 mg/day oral prednisone or equivalent.
 
Asymptomatic with amylase and/or lipase >2.0–5.0 × ULN:
Treat as a Grade 3 event.
 | 
Continue atezolizumab & CDX-1127 (varlilumab) and cobimetinib.
 
Monitor amylase and lipase weekly.
 
For prolonged elevation (e.g., >3 weeks), consider treatment with 10 mg/day oral prednisone or equivalent.
 
Asymptomatic with amylase and/or lipase >2.0–5.0 × ULN:
Treat as a Grade 3 event.
 |
|                                 | Grade 3 or 4 | Hold atezolizumab & CDX-1127 (varlilumab).  | Hold atezolizumab & CDX-1127 (varlilumab) and cobimetinib.  |

|        |   |  |  |
|--------|---|--|--|
|        |   | 
Refer patient to gastrointestinal (GI) specialist.
 
Monitor amylase and lipase every other day.
 
If no improvement, consider treatment with 1–2 mg/kg/day oral prednisone or equivalent.
 
If event resolves to grade 1 or better within 12 weeks, taper corticosteroids and resume atezolizumab & CDX-1127 (varlilumab) according to the guidelines above.
 
Permanently discontinue atezolizumab & CDX-1127 (varlilumab) if event does not resolve to grade 1 or better within 12 weeks.
 
For recurrent events, permanently discontinue atezolizumab & CDX-1127 (varlilumab).
 | 
Refer patient to gastrointestinal (GI) specialist.
 
Monitor amylase and lipase every other day.
 
If no improvement, consider treatment with 1–2 mg/kg/day oral prednisone or equivalent.
 
If event resolves to grade 1 or better within 12 weeks, taper corticosteroids and resume atezolizumab & CDX-1127 (varlilumab) at previous fixed and cobimetinib with 1 dose-level reduction.
 
Permanently discontinue atezolizumab & CDX-1127 (varlilumab) and cobimetinib if event does not resolve to grade 1 or better within 12 weeks.
 
For recurrent events, permanently discontinue atezolizumab & CDX-1127 (varlilumab) and cobimetinib.
 |
| Anemia | Grade 3

Without presence of active hemorrhage or immune-mediated hemolysis | 
Continue atezolizumab & CDX-1127 (varlilumab).
 
Transfuse prn to Grade <math>\leq 2</math> or resolution of symptomatic anemia
 
Monitor CBC weekly
  | 
Continue atezolizumab & CDX-1127 (varlilumab) and cobimetinib
 
Transfuse prn to Grade <math>\leq 2</math> or resolution of symptomatic anemia
   |

|   |  |  |  |
|---|--|--|--|
|   |  | Workup for etiologies of anemia  | Monitor CBC weekly

Workup for etiologies of anemia

For recurrent grade 3 anemia, can consider 1 dose level reduction for cobimetinib   |
| Cardiac Event – Decreased Left Ventricular Ejection Fraction (LVEF) | Asymptomatic, absolute decrease in LVEF from baseline of greater than 10% and LVEF less than 50% | 
Hold atezolizumab & varlilumab. Assess for symptoms and complete work up. Repeat ECHO in 2 weeks.
 
Work up should generally include troponin, CPK, EKG, echocardiogram and/or cardiac MRI, and cardiology consultation
 
Resume atezolizumab & CDX-1127 (varlilumab) at fixed dose if all of the following are present
 
 
• LVEF is 50% or greater, OR
 
• Absolute decrease from baseline LVEF is more than 10%
 
 
Permanently discontinue atezolizumab & CDX-1127 (varlilumab)* if any of the following are present
 
 
• LVEF is 50% or greater, AND
 
• Absolute decrease from baseline LVEF is more than 10%
 
 
* If etiology of
 | 
Hold atezolizumab, CDX-1127 (varlilumab), and cobimetinib. Assess for symptoms and complete work up. Repeat ECHO in 2 weeks.
 
Work up should generally include troponin, CPK, EKG, echocardiogram and/or cardiac MRI, and cardiology consultation
 
Resume atezolizumab & CDX-1127 (varlilumab) at fixed dose and cobimetinib at next lower dose if all of the following are present
 
 
• LVEF is 50% or greater, OR
 
• Absolute decrease from baseline LVEF is more than 10%
 
 
Permanently discontinue atezolizumab & CDX-1127 (varlilumab)* and cobimetinib any of the following are present
 
 
• LVEF is 50% or greater, AND
 
• Absolute decrease from
 
 |

|  |   |  |   |
|--|---|--|---|
|  |   | 
decreased LVEF can be confidently attributed to a non-immune-mediated etiology, LVEF is > 40% (or <math>\leq</math> 10% absolute decrease from BL) and myocarditis has been excluded, resumption of atezolizumab & CDX-1127 (varlilumab) at fixed dose can be considered on case by case basis with discussion & approval by trial PI. For patients with more severe reductions in the LVEF, atezolizumab & CDX-1127 (varlilumab) may be restarted only if the patient is clinically stable, and after consultation with the trial PI.
 | 
baseline LVEF is more than 10%
 
*If etiology of decreased LVEF can be confidently attributed to cobimetinib alone or a non-immune-mediated etiology, LVEF is > 40% (or <math>\leq</math> 10% absolute decrease from BL) and myocarditis has been excluded, resumption of atezolizumab & CDX-1127 (varlilumab) at fixed dose can be considered on case by case basis with discussion & approval by trial PI. For patients with more severe reductions in the LVEF, atezolizumab & CDX-1127 (varlilumab) may be restarted only if the patient is clinically stable, and after consultation with the trial PI.
 |
|  | Symptomatic LVEF decrease from baseline | 
Withhold atezolizumab & CDX-1127 (varlilumab) for up to 4 weeks; repeat LVEF
 
Work up should generally include troponin, CPK, EKG, echocardiogram and/or cardiac MRI, and cardiology consultation
 
Resume atezolizumab & CDX-1127 (varlilumab) at fixed dose if all of the following are present
 
 
• Symptoms
 
   | 
Withhold atezolizumab & CDX-1127 (varlilumab) and cobimetinib for up to 4 weeks; repeat LVEF
 
Work up should generally include troponin, CPK, EKG, echocardiogram and/or cardiac MRI, and cardiology consultation
 
Resume atezolizumab & CDX-1127 (varlilumab) at fixed dose and cobimetinib at next
   |

|  |  |  |   |
|--|--|--|---|
|  |  | 
resolved, and
 
 
• LVEF is 50% or greater, OR
 
• Absolute decrease from baseline LVEF is 10% or less
 
 
Permanently discontinue atezolizumab & CDX-1127 (varlilumab)* if any of the following are present
 
 
• Symptoms persist, or
 
• Symptoms resolved, but LVEF is less than 50% and Absolute decrease from baseline LVEF is more than 10%
 
 
* If etiology of decreased LVEF can be confidently attributed to a non-immune-mediated etiology, LVEF is > 40% (or <math>\leq</math> 10% absolute decrease from BL) and myocarditis has been excluded, resumption of atezolizumab & CDX-1127 (varlilumab) at fixed dose can be considered on case by case basis with discussion & approval by trial PI. For patients with more severe reductions in the LVEF, atezolizumab & CDX-1127 (varlilumab) may be restarted only if the patient is clinically stable, and after
 | 
lower dose if all of the following are present
 
 
• Symptoms resolved, and
 
• LVEF is 50% or greater, OR
 
• Absolute decrease from baseline LVEF is 10% or less
 
 
Permanently discontinue atezolizumab & CDX-1127 (varlilumab)* and cobimetinib any of the following are present
 
 
• Symptoms persist, or
 
• Symptoms resolved, but LVEF is less than 50% and Absolute decrease from baseline LVEF is more than 10%
 
 
*If etiology of decreased LVEF can be confidently attributed to cobimetinib alone or a non-immune-mediated etiology , LVEF is > 40% (or <math>\leq</math> 10% absolute decrease from BL) and myocarditis has been excluded, resumption of atezolizumab & CDX-1127 (varlilumab) at fixed dose can be considered on case by case basis with discussion & approval by trial PI. For patients with more severe reductions in the LVEF,
 |
|--|--|--|---|

|                                 |   |   |   |
|---------------------------------|---|---|---|
|                                 |   | consultation with and approval from the trial PI.   | atezolizumab & CDX-1127 (varlilumab) may be restarted only if the patient is clinically stable, and after consultation with and approval from the trial PI.   |
| Creatine Kinase (CPK) Elevation | General Guidance  | 
Rule out cardiac cause (check ECG, serum cardiac troponin, and CPK-isoforms M and B fraction) and rule out rhabdomyolysis (clinical examination; serum creatinine, potassium, calcium, phosphorus, uric acid, and albumin; and urine myoglobin).
 
Permanently discontinue atezolizumab & CDX-1127 (varlilumab) if there is evidence of clinically significant cardiac injury or rhabdomyolysis.. Assess patient for any history of strenuous physical activity, blunt trauma, or recent IM injections.
 | 
Rule out cardiac cause (check ECG, serum cardiac troponin, and CPK-isoforms M and B fraction) and rule out rhabdomyolysis (clinical examination; serum creatinine, potassium, calcium, phosphorus, uric acid, and albumin; and urine myoglobin).
 
Permanently discontinue atezolizumab & CDX-1127 (varlilumab) and cobimetinib if there is evidence of clinically significant cardiac injury or rhabdomyolysis.
 
Assess patient for any history of strenuous physical activity, blunt trauma, or recent IM injections.
 |
|                                 | Grade 3 that are asymptomatic and deemed not clinically significant | 
Hold atezolizumab & CDX-1127 (varlilumab) pending workup to rule out immune related cardiomyopathy, myocarditis or other cardiac conditions.
 
Workup should generally include ECG, serum cardiac troponin, and CPK-isoforms M and B fraction.
 
Atezolizumab & CDX-
   | 
Hold atezolizumab & CDX-1127 (varlilumab) and cobimetinib pending workup to rule out immune related cardiomyopathy, myocarditis or other cardiac conditions.
 
Workup should generally include ECG, serum cardiac troponin, and CPK-isoforms M and B fraction.
  |

|  |   |  |  |
|--|---|--|--|
|  |   | 
1127 (varlilumab) at fixed dosage only if cardiac etiology is ruled out.
 
Recheck CPK at least once a week. If CPK remains Grade 3 or decreases, continue Atezolizumab & CDX-1127 (varlilumab) at fixed dosage.
   | 
Atezolizumab & CDX-1127 (varlilumab) and cobimetinib may be restarted at previous dose and schedule only if cardiac etiology is ruled out.
 
Recheck CPK at least once a week. If CPK remains Grade 3 or decreases, continue Atezolizumab & CDX-1127 (varlilumab) and cobimetinib at fixed dosage and cobimetinib at current dose and schedule.
  |
|  | 
Grade 4 CPK elevations or any grade CPK with clinically significant effect (signs of cardiac injury and/or renal injury)
 | 
Hold atezolizumab & CDX-1127 (varlilumab). Work up and treat per institutional guidelines. Rule out immune-related cardiomyopathy, myocarditis, other cardiac conditions, and myoglobin-induced kidney injury.
 
Recheck CPK within 3 days. When CPK is Grade <math>\leq</math> 3 and cardiac immune-related cardiomyopathy has been ruled out, atezolizumab & CDX-1127 (varlilumab) may be resumed
 
Permanently discontinue atezolizumab & CDX-1127 (varlilumab) if Grade 4 CPK elevation recurs or if there is evidence of cardiac/renal
 | 
Hold atezolizumab & CDX-1127 (varlilumab) and cobimetinib. Work up and treat per institutional guidelines. Rule out immune-related cardiomyopathy, myocarditis, other cardiac conditions, and myoglobin-induced kidney injury.
 
Recheck CPK within 3 days. When CPK is Grade <math>\leq</math> 3 and cardiac immune-related cardiomyopathy has been ruled out, atezolizumab & CDX-1127 (varlilumab) and cobimetinib may be resumed with a dose reduction of cobimetinib by 1 dose level on the same schedule (e.g., 60 to 40 mg).
 
If Grade 4 CPK
 |

|   |         |  |  |
|---|---------|--|--|
|   |         | 
injury with any instance of CPK elevation*.
 
*If non-immune related etiology is most likely, resumption of atezolizumab & CDX-1127 (varlilumab) at fixed dose will require consultation with and approval by study PI
 | 
elevation recurs after 1 dose reduction, cobimetinib may be reduced by another dose level (e.g., 40 to 20 mg).
 
Permanently discontinue atezolizumab & CDX-1127 (varlilumab) and cobimetinib if Grade 4 CPK elevation recurs after 2 dose reductions of cobimetinib OR if there is evidence of cardiac/renal injury associated with any instance CPK elevation.
 
*If non-immune related etiology is most likely, resumption of atezolizumab & CDX-1127 (varlilumab) at fixed dose without cobimetinib will require consultation with and approval by study PI
 |
| Dermatologic toxicity/rash (e.g., maculopapular or purpura) | Grade 1 | 
Continue atezolizumab & CDX-1127 (varlilumab).
 
Initiate symptomatic therapy with antihistamine PRN.
 
Consider topical steroids and/or other symptomatic therapy (e.g., antihistamines).
                        | 
Continue atezolizumab & CDX-1127 (varlilumab) and cobimetinib
 
Initiate symptomatic therapy with antihistamine PRN.
 
Consider topical steroids and/or other symptomatic therapy (e.g., antihistamines).
 
For acneiform rash, consider topical corticosteroids (hydrocortisone 2.5%, alclometasone) and oral
   |

|         |   |   |
|---------|---|---|
|         |   | antibiotics (minocycline, doxycycline, or antibiotics covering skin flora) BID for at least 4 weeks.  |
| Grade 2 | 
Continue atezolizumab & CDX-1127 (varlilumab).
 
Consider consultation with a dermatologist for evaluation and if indicated, biopsy.
 
Administer topical steroids.
 
Consider higher potency topical steroids if rash does not improve.
 
For acneiform rash, topical corticosteroids (hydrocortisone 2.5%, alclometasone) and oral antibiotics (minocycline, doxycycline, or antibiotics covering skin flora) BID for at least the first 6 weeks
 | 
Continue atezolizumab & CDX-1127 (varlilumab) and cobimetinib.
 
Consider consultation with a dermatologist.
 
Administer topical steroids.
 
Consider higher potency topical steroids if rash does not improve.
 
For acneiform rash, administer topical corticosteroids (hydrocortisone 2.5%, alclometasone) and oral antibiotics (minocycline, doxycycline, or antibiotics covering skin flora) for at least the 6 weeks.
 
For an initial grade 2 rash that is considered attributable to Cobimetinib and remains grade 2 at the start of the next cycle, despite appropriate topical treatments and oral antibiotics, continue atezolizumab & CDX-1127 (varlilumab) at fixed dose, but can consider holding cobimetinib until resolution to grade 1 or
 |

|         |  |   |
|---------|--|---|
|         |  | lower. Cobimetinib should be reduced one dose level.  |
| Grade 3 | 
Hold atezolizumab & CDX-1127 (varlilumab). Refer patient to dermatologist for evaluation and if indicated, biopsy.
 
Administer oral prednisone 10 mg or equivalent. If the event does not improve within 48–72 hours, increase dose to 1–2 mg/kg/day or equivalent.
 
Restart atezolizumab & CDX-1127 (varlilumab) if event resolves to grade 2 (tolerable) or better within 12 weeks.
 
Permanently discontinue atezolizumab & CDX-1127 (varlilumab) if event does not resolve to tolerable grade 2 or better within 12 weeks.
 | 
Hold atezolizumab & CDX-1127 (varlilumab) and cobimetinib.
 
Refer patient to dermatologist.
 
Administer oral prednisone 10 mg or equivalent if the rash is at least possibly attributable to the atezolizumab therapy. If the event does not improve within 48–72 hours, increase dose to 1–2 mg/kg/day or equivalent.
 
For acneiform rash, consider continuation of topical corticosteroids (2.5%, alclometasone) and oral antibiotics (minocycline, doxycycline or antibiotics covering skin flora) for at least 6 weeks
 
Restart atezolizumab & CDX-1127 (varlilumab) at fixed dose and cobimetinib at 1 dose reduction if rash resolves to <math>\leq</math> tolerable grade 2, and systemic dose is less than or equal to 10 mg oral prednisone equivalent per day.
 |
| Grade 4 | Permanently discontinue atezolizumab & CDX-1127 (varlilumab).  | Permanently discontinue atezolizumab & CDX-1127 (varlilumab) and  |

|                     |  |   |  |
|---------------------|--|---|--|
|                     |  | Patient may not resume treatment, regardless of benefit. Otherwise, manage as above.   | cobimetinib. Patient may not resume treatment, regardless of benefit. Manage as above.   |
|                     | Persistent and/or severe rash or pruritus, any grade               | A dermatologist should evaluate the event. A biopsy should be performed unless contraindicated.   | A dermatologist should evaluate the event. A biopsy should be performed unless contraindicated.  |
